6.4.3 Staged Procedures

6.4.4 Planned staged procedures are not allowed. All non-target lesions should be treated prior to target lesion treatment; as specified in section 6.4.2 Pre-Dilation of Target Lesion(s)

Pre-dilation is recommended but not required. Pre-dilation can be performed per study stent labeling and per local standards. An angioplasty balloon, cutting balloon, angiosculpt scoring balloon, or atherectomy can be utilized for pre-dilation. The pre-dilation balloon should be shorter than the planned stent(s) length to limit pre-dilation injury within the area to be stented. It is recommended that a pre-dilation catheter that is 0.5 mm smaller in diameter than the reference vessel is used.

6.4.5 Study Stent Use

Prior to use, the study stent will be inspected and prepared according to the applicable Instructions for Use.

- There is no limit to the number of lesions per vessel or individual lesion length.
- If more than one lesion in the same epicardial vessel is treated, it is recommended that stenting be initiated distally and progress proximally.
- Overlapping stents are allowed as long as the first stent implanted is the EluNIR 38 mm long stent. It is recommended that the distal stent should be deployed first, followed by deployment of the proximal stent, to reduce the risk of dislodging the proximal stent.
- Stent sizing should follow a stent: artery ratio of 1.1:1 per operator's visual estimate.
- Brachytherapy must NOT be performed in conjunction with the baseline procedure.
- Post-dilation is strongly recommended, and when performed should only be performed with balloon lengths that fit within the boundaries of the stent. Do not exceed the rated burst pressure as indicated in the product labeling of the study stents. The vessel size and lesion length should be assessed after post-dilation. An optimal stent result is final diameter stenosis of <20% by operator's visual estimate.

6.4.6 Treatment Failures and Device Malfunctions

In case of failure to deliver the study stent, typical measures should be undertaken to ensure the lesion has been adequately prepared, such as use of appropriately sized pre-dilatation balloons, cutting or scoring balloons, and/or rotational atherectomy as appropriate. Guide catheter support should be optimized using standardized techniques, including use of buddy wires and/or guide extension devices as appropriate. If the study stent can still not be delivered, any commercially available stent may be used to successfully and safely complete the procedure.

All failures and EluNIR malfunctions will be documented on the appropriate CRF if the patient has been enrolled to the study. The EluNIR should be returned to Medinol for analysis and be reported in the clinical results. Instructions for returning the EluNIR are included in the trial's operations manual. Treatment failures or device malfunctions should be reported in the CRF within 24 hours, per the instructions of EDC completion.

6.4.7 Bail-out Stenting Procedures

Bailout stenting may be performed at the operator's discretion. If a bailout stent is required, EluNIR stent of an appropriate diameter and length must be used. If EluNIR of appropriate length and diameter is not available, an approved coronary stent should be used, preferably a second generation DES.

6.4.8 Concomitant Medications

6.4.8.1 Pre-Procedure (Loading) Anti-Platelet Medication

Loading doses of anti-platelet medications should be administered pre-procedure in all patients as shown in [Table 4](#) and according to the local standards.

Table 4: Recommended Pre-Procedure Anti-Platelet Medication Regimen

Agent	Instructions
Clopidogrel	A loading dose of clopidogrel 600mg must be administered between 0 to 24 hours prior to PCI or immediately post PCI (administration prior to PCI is preferred in all patients). For subjects who are already on chronic clopidogrel therapy of 75 mg (\geq 5 days), a loading dose of 300 mg is required in all patients between 0 to 24 hours prior to PCI or immediately post PCI (administration prior to PCI is preferred in all patients).
OR Prasugrel	At sites in countries where prasugrel is approved and is commercially available, a loading dose of prasugrel 60 mg can be used in place of clopidogrel at the investigator's discretion. For subjects already on chronic prasugrel therapy of 10mg a day (5mg if >75 years old or <60 kg weight) for \geq 5 days a loading dose of prasugrel 60mg is recommended at the investigator's discretion.
OR Ticagrelor	At sites in countries where ticagrelor is approved and commercially available, a loading dose of ticagrelor 180 mg can be used in place of clopidogrel at the investigator's discretion. For subjects already on chronic ticagrelor therapy of 90mg twice daily for \geq 5 days a loading dose of ticagrelor 180mg is recommended at the investigator's discretion.
Aspirin	All subjects already taking daily chronic aspirin therapy will receive 75-325mg or dose per standard hospital practice before the procedure. Subjects not already taking daily chronic aspirin therapy will receive 300 to 325mg (or dose per standard hospital practice) at least two hours and preferably 24 hours before the procedure.

6.4.8.2 Anticoagulation during Baseline Procedure

PCI should be performed with adequate anticoagulation. Unfractionated heparin (UFH), low-molecular weight heparin (LMWH) or bivalirudin may be used with additional glycoprotein inhibitor (GPI) according to local standards.

6.4.8.3 Post-Procedure Anti-Platelet Medication

Dual anti-platelet therapy should be instituted post procedure in all patients as shown in [Table 5](#).

All subjects are required to have clopidogrel/prasugrel/ticagrelor administration for a minimum of 6 months (12 months in ACS patients) as well as aspirin administration indefinitely unless an intervening medical necessity occurs such as severe bleeding.

Table 5: Post-Procedure Anti-Platelet Medication Regimen

Agent	Instructions
Clopidogrel	All subjects who receive a study stent will be treated for a minimum of six months of clopidogrel (75 mg/day) and up to 12 months following stent implantation, per the AHA/ACCF/SCAI joint guidelines for percutaneous coronary intervention.(1)
OR Prasugrel	At sites in countries where prasugrel is approved and is commercially available, prasugrel 10 mg/day can be used in place of clopidogrel at the investigator's discretion. In subjects weighing less than 60 kg or who are over 75 years old, prasugrel should be given at a dose of 5 mg/day.
OR Ticagrelor	At sites in countries where ticagrelor is approved and is commercially available, ticagrelor 90 mg bid can be used in place of clopidogrel at the investigator's discretion.
Aspirin	Subjects with no aspirin resistance, allergy, or bleeding risk should continue on aspirin (minimum of 75 mg/day and up to 162 mg/day or dose per standard hospital practice) indefinitely, in accordance with the AHA/ACC/SCAI PCI recommendations. Low-dose aspirin (<100 mg/day) is preferred in all patients. Higher doses should not be used with ticagrelor.

6.4.9 Activities Performed by Sponsor Representatives

No activities other than monitoring will be performed by the Sponsor representatives.

6.4.10 Known or Foreseeable Factors That May Compromise the Outcome

Factors that may compromise the outcome are lack of enrollment and poor data collection.

6.5 Monitoring Plan

6.5.1 Monitoring

Sponsor and/or designee will monitor the trial over its duration according to the pre-specified monitoring plan. The trial monitor will visit each site at appropriate intervals to review investigational data for accuracy and completeness and ensure compliance with the clinical investigation plan. The trial monitor may inspect all documents and required records that are maintained by the Investigator/Site, including medical records (office, clinic, or hospital) for the subjects in this trial. Source documentation must be available to substantiate proper informed consent procedures, adherence to clinical investigation plan procedures, adequate reporting and follow-up of adverse events, accuracy of data collected on case report forms, and device information. A monitoring visit sign-in log will be maintained at the site. The Investigator and/or research coordinator will be available for monitoring visits. It is expected that the Investigator/Site will provide the trial monitor with a suitable working environment for review of study-related documents.

6.5.2 Identification of Data Recorded on CRF and Considered Source Data

The Investigator is responsible for maintaining complete and accurate documentation of the trial including but not limited to medical records, trial progress records, laboratory results, case report forms, signed informed consent forms, device accountability records, correspondence with the EC as well as trial monitors and sponsor, adverse event reports, and information regarding subject discontinuations.

The Investigator is required to maintain information in the subject's medical records which documents and corroborates data entered in the case report forms. As a minimum the subject record should contain:

- Medical history/physical exam documenting that subject meets inclusion/exclusion criteria
- Documentation of subject's consent and subject ID number in the trial
- Dated and signed notes from each subject visit
- Adverse events reported and their resolution or lack thereof including supporting documents such as hospital records, discharge summaries, catheterization reports, ECGs, etc.
- Record of clinical investigation plan required medications during the trial
- Record of the subject's condition upon completion of or withdrawal from the trial

6.5.3 Direct Access to Source Data/Documents

The Investigator and the associated institution will permit direct access to source data/documents for study-related monitoring, audits, EC review and regulatory inspections.

Subjects providing informed consent agree to allow the Sponsor or designee access and copying rights to pertinent information in their medical records concerning their participation in this trial. The Investigator will obtain, as part of the informed consent, permission for trial monitors or regulatory authorities to review, in confidence, any records identifying the subjects in this trial. This information may be shared with regulatory agencies; however, the Sponsor undertakes not to otherwise release the patient's personal and private information.

6.5.4 Training

6.5.4.1 Site Training

All Investigators and trial personnel are required to attend Sponsor training sessions, which may be conducted at an Investigator's meeting, a site initiation visit, or other appropriate training sessions including training utilizing electronic media. Training of Investigators and trial personnel will include, but is not limited to, the investigational plan, study device, case report form completion and trial personnel responsibilities. All Investigators and trial personnel who are trained must sign a training log (or an equivalent) upon completion of the training. Investigator and trial personnel must not perform any study-related procedures prior to being trained. All Investigators must be trained to the clinical investigation plan and trial procedures prior to enrolling subjects.

6.5.4.2 Training of Sponsor's Monitors

The Sponsor's monitors or designee will be trained to the clinical investigational plan, case report forms, and study device usage. The Sponsor or designee is responsible for the training. Training will be conducted in accordance with the Sponsor's and/or designee's standard procedures.

6.5.5 Quality Assurance Assessments

The Sponsor and/or designee may conduct periodic compliance assessments (on-site audits) at various study sites. A Sponsor representative or designee may request access to all trial records, including source documentation, for inspection and duplication during a compliance assessment. The Investigator and research coordinator must be available to respond to reasonable requests and queries made during the compliance assessment process.

6.5.6 Regulatory Agency Inspection

In the event that an Investigator is contacted by a Regulatory Agency in relation to this trial, the Investigator will notify the Sponsor immediately. The Investigator and research coordinator must be available to respond to reasonable requests and inspection queries made during the inspection process. The Investigator must provide the Sponsor with copies of all correspondence that may affect the review of this trial. The Sponsor will provide any needed assistance in response to regulatory inspections.

7 STATISTICAL CONSIDERATIONS

7.1 Statistical Design

This is a prospective, multi-center, single arm, open label, clinical trial that is descriptive in nature. The Trial will enroll approximately 50 subjects with a wide spectrum of PCI indications (stable angina as well as ACS, including subacute STEMI (>24 hours since first hospital presentation) as well as complexity. This sample size (n=50) provides 80% power to observe at least one device related AE if occurring with an incidence of 3.2%.

Among 50 patients, we will have > 80% probability to detect at least one event from any events with a rate above 3.2% . Mathematically, we compute the probability (assuming Binomially distributed events) as

$$\begin{aligned} p(\text{Event} > 0) &= 1 - p(\text{Event} = 0) \\ 0.80 &= 1 - (1 - p)^{50} \\ p &= 1 - (1 - 0.80)^{1/50} \end{aligned}$$

7.2 Analysis and Reporting of Results

7.2.1 Methods

All statistical analysis will be performed using Statistical Analysis System (SAS) (version 9.2 or higher) or other widely accepted statistical or graphical software. Subject data listings and tabular and/or graphical presentations of results will be provided.

Descriptive statistics will be used to generate an overall summary of the study endpoints, baseline and procedural variables, and clinical outcomes. Continuous variables will be presented as means, standard deviations, medians, first and third quartiles, minimums, maximums, and 95% confidence intervals for the means. For categorical variables, the number within each category and the percentage out of the total number of available observations will be summarized.

7.2.2 Analysis of Primary Endpoint

The primary endpoint of device success as determined by the Angiographic Core Lab (ACL) with no 30 day MACE will be summarized descriptively with patient counts, percentages, and 95% exact Binomial confidence intervals. This analysis will be performed using the Full Analysis Set (FAS) as the primary analysis set; however, an analysis in the per-protocol (PP) population will also be performed.

The following additional definitions will be used to assess peri-procedural MIs for the purpose of sensitivity analyses for the primary 30 day MACE endpoint:

- The 3rd Universal Definition of MI definition
- A modification of the SCAI definition of periprocedural MI that utilizes a threshold CK-MB of $\geq 5x$ ULN (rather than $\geq 10x$) in subjects with a normal baseline CK-MB without a requirement for associated clinical signs or symptoms
- A modification of the SCAI definition of periprocedural MI that utilizes a threshold CK-MB of $\geq 3x$ (rather than $\geq 10x$) in subjects with a normal baseline CK-MB without a requirement for associated clinical signs or symptoms

7.2.3 Analysis of Secondary Endpoints

Analysis of the secondary endpoints will be performed on the FAS population. Data for all categorical endpoints will be summarized with patient counts, percentages, and exact 95% confidence intervals. Data for all continuous endpoints will be summarized with descriptive statistics (means, medians, standard deviations, minimums, maximums, and 95% confidence intervals for the means).

7.2.4 Poolability of Data

No adjustment for multiple centers is necessary, as this study is descriptive in nature.

7.2.5 Multiple Comparisons/Multiplicity

No adjustments for multiple comparisons/multiplicity are necessary, as this study is descriptive in nature.

There are no planned interim analyses prior to the primary endpoint.

7.3 Criteria for Termination of the Clinical Investigation

There are no stopping rules for the trial. The EluNIR Program (BIONICS and NIREUS Trials) DSMB will review data from this study.

7.4 Procedures for Reporting Any Deviation(s) from the Original Statistical Plan

Details of the statistical analysis will be outlined in a trial-specific Statistical Analysis Plan (SAP). Any changes to planned analyses will be described and justified in the SAP and noted in the final trial report.

7.5 Specification of Subgroups for Analysis

No subgroups analysis will be performed for the primary endpoint of Device Success.

7.6 Procedures That Take into Account All the Data

The analysis of the primary endpoint will be performed using the following datasets, as appropriate:

- **Full Analysis Set (FAS):** All subjects who have been enrolled into the trial, regardless of whether they received the study stent or not. Subjects are included in the FAS once the stent has been advanced beyond the guide catheter. If the study stent is not advanced beyond the guiding catheter, the patient will be de-registered and will not be considered part of the full analysis set.
- **Per-Protocol (PP) Analysis Set:** All subjects in the Full Analysis Set (FAS) with no major protocol deviations will be included in the Per-Protocol Analysis Set. Major protocol deviations include, but are not limited to, enrollment of a subject:
 - ✓ whose informed consent was not properly obtained
 - ✓ who did not meet all of the inclusion or exclusion criteria
 - ✓ who did not receive at least 6 months of DAPT post baseline procedure
- **Safety Analysis Set:** The safety analysis set will include all subjects, including de-registered subjects, who signed an informed consent and who had any trial-related activities.

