6.1.3.1 Primary Endpoint

Combined efficacy and safety endpoint:

Device success as determined by the Angiographic Core Lab (ACL) with no 30 day MACE.

Device success is defined as achievement of a final in-stent residual diameter stenosis of <30% (by QCA), using the EluNIR 38 mm stent only and without a device malfunction.

MACE is defined as the composite of cardiac death, any MI, or ischemia-driven TLR.

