Procedure success is defined as achievement of a final in-stent diameter stenosis of <30% (by QCA) using the assigned device and/or with any adjunctive devices, without the occurrence of cardiac death, Q wave or non-Q wave MI, or repeat revascularization of the target lesion during the hospital stay.

ADVERSE DEVICE EFFECTS

See Section 14 for definitions of adverse device effects (serious, anticipated, and unanticipated)

ADVERSE EVENTS

See Section 14 for definitions of adverse events (non-serious and serious)

ANALYSIS DATA SETS

Full Analysis Set (FAS)

If the study stent is not advanced beyond the guiding catheter, the patient will be de-registered and will not be considered part of the full analysis set. Patients not receiving the study stent after it has been advanced beyond the guiding catheter will be analyzed in the full analysis set. Patients enrolled in the trial with major deviations will also be analyzed in the full analysis set.

Per Protocol (PP Population)

Patients who receive the study stent with no major protocol deviations as detailed in Section 7.6 will be included in the Per Protocol Analysis Set.

Safety Analysis Set

The safety analysis set will include all subjects who signed an informed consent and have had any trial related activities including de-registered subjects.

ANGINA PECTORIS

CCS Classification of Stable Angina

- I. Ordinary physical activity does not cause angina, such as walking or climbing stairs. Angina occurs with strenuous or rapid or prolonged exertion at work or recreation.
- II. Slight limitation of ordinary activity. Angina occurs upon walking or climbing stairs rapidly, walking uphill, walking or stair climbing after meals, or in cold, or in wind, or under emotional stress, or only during the few hours after awakening. Angina occurs if walking more than two blocks on the level or climbing more than one flight of ordinary stairs at a normal pace and in normal conditions.

III. Marked limitation of ordinary activity. Angina occurs upon walking one or two blocks on the level or climbing one flight of stairs in normal conditions and at a normal pace.

IV. Inability to carry on any physical activity without discomfort. Angina syndrome may be present at rest.

Braunwald Classification of Unstable Angina

Severity		Clinical Circumstances		
		A	B	C

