PERCUTANEOUS CORONARY INTERVENTION (PCI)

Refers to all interventional cardiology methods for treatment of coronary artery disease.

PERFORATION

Perforations will be classified as follows:

- Angiographic perforation: perforation detected by the clinical site or the core laboratory at any point during the procedure.
- Clinical perforation: perforation requiring additional treatment (including efforts to seal the perforation or pericardial drainage), or resulting in significant pericardial effusion, abrupt closure, myocardial infarction, or death.
- Pericardial hemorrhage/tamponade: perforation resulting in cardiac tamponade.

PERSISTING DISSECTION

Dissection at follow-up that was present post baseline procedure.

PRIMARY INVESTIGATOR

The physician responsible for conducting the clinical trial at each investigational site.

PRINCIPAL INVESTIGATOR

A physician-specialist, related to the trial, who is responsible for the overall conduct of the trial at all sites and compliance with clinical investigation plan and relevant regulations.

PROTOCOL DEVIATIONS - MAJOR

Major protocol deviations include, but are not limited to, enrollment of a subject:

- Whose informed consent was not properly obtained
- Who did not meet all of the inclusion or exclusion criteria
- Who did not receive at least 6 months of DAPT post baseline procedure

REFERENCE VESSEL DIAMETER (RVD)

Average diameter of proximal and distal healthy segments by QCA. 10 mm “normal” reference segments are selected proximal and distal to the stenosis and averaged to define the reference vessel diameter. A computer-defined interpolated normal segment will be used to calculate percent diameter stenosis.

RESTENOSIS

Re-narrowing of the artery following the removal or reduction of a previous narrowing.

REVASCULARIZATION (per ARC definition, Circulation 2007;115:2344-51)

Target Lesion Revascularization (TLR)

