1.0 INTRODUCTION

This Statistical Analysis Plan (SAP) provides the detailed methodology for summary and statistical analyses of the data collected in BIONICS 38 mm trial. This document may modify the plans outlined in the protocol; however, any major modifications of the primary endpoint definition or its analysis will also be reflected in a protocol amendment. This plan is based on the trial protocol version 1.1.

The primary endpoint analysis for the BIONICS 38 mm trial will be performed after all patients have completed the 30-day follow-up assessment. The secondary long-term endpoints will be assessed separately after all patients have completed the 1 year follow-up assessment and will not be part of the Clinical Study Report (CSR).

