3.0 ANALYSIS SETS

Full Analysis Set (FAS): All subjects who have been enrolled into the trial, regardless of whether they received the study stent or not will be included in the FAS. Subjects are included in the FAS once the EluNIR 38 mm stent has been advanced beyond the guide catheter. If the study stent is not advanced beyond the guiding catheter, the patient will not be enrolled in the trial.

Per-Protocol (PP) Population: All subjects in the Full Analysis Set (FAS) with no major protocol deviations as identified by the Medical Monitor will be included in the Per-Protocol Analysis Set. Major protocol deviations may include the following categories:

- Informed consent was not properly obtained
- Inclusion or exclusion criteria deviations
- Not receiving DAPT post-baseline procedure according to the standard of care

Major protocol deviations will be identified by the Medical Monitor prior to the database lock for the primary analysis.

Safety Analysis Set: All subjects, including subjects who are consented but do not meet eligibility criteria and not in the FAS will be included in the Safety Analysis Set. Safety Analysis Set will also include all FAS patients.

Table 2 summarizes the analysis sets to be used for each type of analyses.

 Cardiovascular Research Foundation	FORM		Document N° BIO-TMP-0702 Revision: 00
	TITLE SAP Template		Effective date: 16-Mar-2018 Department: BIO

Table 2 Analyses and analysis sets

Endpoint	FAS	PP Analysis Set	Safety Analysis Set
Primary endpoint	X	X	
Secondary endpoints	X	X	
AEs, Other Safety Data			X
Demographics/baseline characteristics	X		
Angiographic Core Lab Analysis	X		

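### The per-protocol set for the 30-day primary endpoint is inconsistent on two conditions: receipt of the study stent, and the DAPT criterion

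*Protocol*

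**What the plan says.** Protocol 7.2.2 makes the FAS the primary set for the primary endpoint and adds a PP analysis. SAP 3.0, Table 2, marks both sets for that endpoint.

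Protocol 7.6 builds PP from FAS subjects without a major protocol deviation. Its open-ended list of such deviations includes enrolling a subject "who did not receive at least 6 months of DAPT post baseline procedure". The list of major deviations in protocol 19.1 repeats the item: "Who did not receive at least 6 months of DAPT post baseline procedure".

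The analysis-set entry in protocol 19.1 words PP differently: "Patients who receive the study stent with no major protocol deviations as detailed in Section 7.6". The same entry says "Patients not receiving the study stent after it has been advanced beyond the guiding catheter will be analyzed in the full analysis set".

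SAP 3.0 again starts from the FAS and sets no stent-receipt condition. Its DAPT category is "Not receiving DAPT post-baseline procedure according to the standard of care", given as one that major deviations may include. On timing it says "Major protocol deviations will be identified by the Medical Monitor prior to the database lock for the primary analysis". SAP 1.0 places the primary analysis after all patients have finished 30-day follow-up.

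Protocol 6.1.3.1 defines device success as a residual stenosis result obtained "using the EluNIR 38 mm stent only and without a device malfunction".

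**The concern.** A pre-specified analysis of the primary endpoint should have one denominator. Here it depends on which passage the programmer follows.

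The stent-receipt condition is not neutral. A subject in whom the stent was advanced but not received has already failed the endpoint, so a rule that removes such subjects removes failures and nothing else. Protocol 6.3.4 has all eligible patients approached whatever the procedural result, in order to limit selection bias. The 19.1 condition works against that aim within PP.

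The 6-month DAPT item has a different problem. Membership of a set used for a 30-day endpoint would depend on treatment received up to five months after that endpoint is known. An early cardiac death, which is itself a primary-endpoint failure, could be read as less than 6 months of DAPT and leave the set. Subjects recently treated at the lock could not yet be confirmed as members.

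**Working it through.** The PP text gives no figure of its own. The only related number is n = 50, for which protocol 7.1 claims 80% probability of seeing at least one event of incidence 3.2%. This reproduces: 1 − (1 − 0.032)^50 = 80.3%. It serves below only as the set size.

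**Step 1. The passages side by side.**

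| Source | Starting set | Stent receipt required | DAPT item |
|---|---|---|---|
| Protocol 7.6 | FAS | No | At least 6 months |
| Protocol 19.1 | Not stated as FAS; uses the 7.6 deviation list | Yes | At least 6 months (through 7.6, and repeated) |
| SAP 3.0 | FAS | No | Standard of care, no duration |

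There are two separate differences: stent receipt (19.1 against 7.6 and the SAP) and DAPT (protocol against SAP).

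**Step 2. Stent receipt.** Let N be the FAS subjects without a major deviation, S the successes, and k the subjects who did not receive the stent. Under 6.1.3.1 none of the k is in S. Protocol 7.6 gives S/N and 19.1 gives S/(N − k). Since N − k ≤ N, the second is never below the first. The documents state no expected rate, so these counts are assumed (exact 95% CI):

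| Delivery failures removed | From 45/50 | From 40/50 | From 48/50 |
|---|---|---|---|
| 0 | 90.0% (78.2 to 96.7) | 80.0% (66.3 to 90.0) | 96.0% (86.3 to 99.5) |
| 1 | 45/49 = 91.8% (80.4 to 97.7) | 40/49 = 81.6% | 48/49 = 98.0% |
| 2 | 45/48 = 93.8% (82.8 to 98.7) | 40/48 = 83.3% | 48/48 = 100% (92.6 to 100) |
| 3 | 45/47 = 95.7% (85.5 to 99.5) | 40/47 = 85.1% (71.7 to 93.8) | not possible (only 2 failures) |

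**Step 3. Direction of the DAPT item.** From 45/50, excluding one failure gives 45/49 = 91.8%; excluding one success gives 44/49 = 89.8% (77.8 to 96.6). The documents give no DAPT discontinuation rate by outcome, so the net direction is unknown.

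**Step 4. Subjects not yet confirmable, if the 6-month item is applied.** Take 6 months as 180 days (SAP 4.3), uniform accrual over A = 365 days (one-year enrolment, protocol 6.3.8) and a lock L days after the last procedure. The share under 180 days from procedure is max(0, 180 − L)/A.

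- L = 30: 150/365 = 41.1%, about 20.5 of 50
- L = 60: 120/365 = 32.9%
- L = 90: 90/365 = 24.7%
- L = 120: 60/365 = 16.4%
- L = 150: 30/365 = 8.2%
- L = 180: 0%

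These are upper bounds, because a subject already excluded for another deviation can be classified at once. No lock date is stated.

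**The case against.** The strongest reply is that the SAP governs. SAP 1.0 says "This document may modify the plans outlined in the protocol", and SAP 3.0 then supplies a rule with neither a 6-month test nor a stent-receipt condition. That is a fair reading, and on it the 41% never arises. But protocol 7.4 requires changes to planned analyses to be described and justified in the SAP. SAP 3.0 offers no reason, the version history records none, and the SAP does not mention the conflict between 7.6 and 19.1. Its own DAPT item is also too loose to apply as a rule.

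A reader might infer that the SAP contains no DAPT duration at all. It does: footnote 5 to SAP Table 3 states minimum durations. SAP 3.0 does not cite that footnote, and importing it would bring the timing problem back.

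A reader might also infer that early deaths will certainly be excluded. The documents do not establish this. Protocol 10.2 defines a deviation as a failure to follow the plan's requirements, and a subject who died, or who is on DAPT at day 60, has arguably failed none. Protocol 4.6 and 6.4.8.3 accept stopping for medical necessity. These point against exclusion, but neither 7.6 nor SAP 3.0 carries them into the PP definition.

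The deviation list in 7.6 is open, so one could argue that non-receipt already falls within it. That is doubtful: inclusion criterion 3 accepts an unsuccessful implant attempt, and 6.4.6 allows another stent after failed delivery.

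**Conclusion.** The inconsistency is real and should be fixed before the primary lock. On stent receipt the direction is certain: relative to 7.6, the 19.1 condition leaves the PP success rate unchanged or raises it. The size depends on the number of delivery failures. It is about 6 percentage points for three failures starting from 45/50, on assumed counts. On DAPT, what is established is an unexplained change of wording and, if the protocol item is read literally, a mismatch between a 6-month criterion and a 30-day analysis. Neither a bias nor its direction is established.

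Three stronger readings are not supported. A reader might count three independent definitions, but 19.1 takes its deviations from 7.6, so there are two differences. A reader might shorten accrual to 183 days by subtracting one year of follow-up from the study span (1 July 2018 to 31 December 2019, 548 − 365), which would raise the 41% to 150/183 = 82%. That contradicts the one-year enrolment in 6.3.8 and treats an approximate end date as fixed. Finally, a reader might see a threat to the main result. There is none: the FAS is primary, PP is supporting, and the trial is descriptive with no hypothesis test.

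**What to change.** Reconcile protocol 7.6, both entries in protocol 19.1 and SAP 3.0 into one PP definition. Record and justify it in the SAP before the primary lock, as 7.4 requires, and align the protocol text at the next amendment.

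- For the 30-day analysis, use only deviations that can be assessed on data through the 30-day visit.
- Do not count death, or a stop that the protocol itself accepts as medical necessity, as a DAPT deviation.
- Keep delivery failures in PP, as 7.6 and SAP 3.0 do. If the 19.1 condition is retained, report how many subjects it removes and give the result with them included.
- State whether the same set applies to the secondary endpoints marked for PP in SAP Table 2, including those at 6 months and 1 year.

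This concerns analysis-set membership only; the DAPT treatment requirement is unchanged. The cost is minor document work with no new data collection, and a PP rate that may be slightly less favourable than under the 19.1 rule.
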